Gynecomastia	Detectable by study participant or caregiver (for young children and disabled adults)	Detectable on physical exam by health care provider	Disfiguring OR Obvious on casual visual inspection	NA
Hyperthyroidism	Asymptomatic	Symptomatic causing greater than minimal interference with usual social & functional activities OR Thyroid suppression therapy indicated	Symptoms causing inability to perform usual social & functional activities OR Uncontrolled despite treatment modification	Life-threatening consequences (eg, thyroid storm)
Hypothyroidism	Asymptomatic	Symptomatic causing greater than minimal interference with usual social & functional activities OR Thyroid replacement therapy indicated	Symptoms causing inability to perform usual social & functional activities OR Uncontrolled despite treatment modification	Life-threatening consequences (eg, myxedema coma)
Lipoatrophy (eg, fat loss from the face, extremities, buttocks)	Detectable by study participant or caregiver (for young children and disabled adults)	Detectable on physical exam by health care provider	Disfiguring OR Obvious on casual visual inspection	NA

GENITOURINARY				
	Grade 1	Grade 2	Grade 3	Grade 4
Intermenstrual Bleeding (IMB)	Spotting observed by participant OR Minimal blood observed during clinical or colposcopic exam	Intermenstrual bleeding not greater in duration or amount than usual menstrual cycle	Intermenstrual bleeding greater in duration or amount than usual menstrual cycle	Hemorrhage with life-threatening hypotension OR Operative intervention indicated
Urinary Tract obstruction (eg, stone)	NA	Signs or symptoms of urinary tract obstruction without hydronephrosis or renal dysfunction	Signs or symptoms of urinary tract obstruction with hydronephrosis or renal dysfunction	Obstruction causing life-threatening consequences

INFECTION				
	Grade 1	Grade 2	Grade 3	Grade 4
Infection (any other than HIV infection)	Localized, no systemic antibacterial treatment indicated AND Symptoms causing no or minimal interference with usual social & functional activities	Systemic antibacterial treatment indicated OR Symptoms causing greater than minimal interference with usual social & functional activities	Systemic antibacterial treatment indicated AND Symptoms causing inability to perform usual social & functional activities OR Operative intervention (other than simple incision and drainage) indicated	Life-threatening consequences (eg, septic shock)

Basic Self-care Functions: Activities such as bathing, dressing, toileting, transfer/movement, continence, and feeding.

Usual Social & Functional Activities: Adaptive tasks and desirable activities, such as going to work, shopping, cooking, use of transportation, pursuing a hobby, etc.

Appendix 5: Pregnancy Precautions, Definition for Female of Childbearing Potential, and Contraceptive Recommendations

Pregnancy and Contraception Requirements for Males and Females of Childbearing Potential

Non-clinical toxicity studies of Epclusa demonstrated no adverse effect on embryo-fetal development. However, there are no clinical studies of Epclusa in pregnant women. Please refer to the latest version of the Investigator's Brochure for additional information.

Definition of Female of Childbearing Potential and Contraceptive Requirements for Female Subjects (and their male partners)

Women >54 years of age with cessation for ≥ 12 months of previously occurring menses, or women of any age who have had a hysterectomy, have had both ovaries removed, or have had medically documented ovarian failure will be considered to be of non-childbearing potential.

Women who are ≤ 54 years of age (including those with amenorrhea of any duration) who have not had a hysterectomy, have not had both ovaries removed, and have not had medically documented ovarian failure will be considered to be of childbearing potential.

Women of childbearing potential must have a negative serum pregnancy test at screening and a negative urine pregnancy test on the Baseline/Day 1 visit prior to enrollment. They must also agree to one of the following from 3 weeks prior to Baseline/Day 1 until 30 days after last dose of study drug:

- 1) Complete abstinence from intercourse. Periodic abstinence (e.g., calendar, ovulation, symptothermal, post-ovulation methods) is not permitted.

Or

- 2) Consistent and correct use of 1 of the following methods of birth control listed below in addition to a male partner who correctly uses a condom from the date of screening until 30 days after last dose of study drug:
 - a) intrauterine device (IUD) with a failure rate of $< 1\%$ per year
 - b) female barrier method: cervical cap or diaphragm with spermicidal agent (if locally available)
 - c) tubal sterilization
 - 3) vasectomy in male partner
 - a) hormone-containing contraceptive:
 - i) implants of levonorgestrel
 - ii) injectable progesterone
 - iii) oral contraceptives (either combined or progesterone only)
 - iv) contraceptive vaginal ring
 - v) transdermal contraceptive patch

3. Contraceptive Requirements for Male Subjects (and their female partners)

All male study participants must agree to consistently and correctly use a condom, while their female partner agrees to use 1 of the methods of birth control listed above, from the date of screening until 90

days after administration of the last dose of study drug:

Male subjects must agree to refrain from sperm donation for at least 90 days after the last dose of study drug.

4. Procedures to be Followed in the Event of Pregnancy

Subjects will be instructed to notify the Investigator if they become pregnant at any time during the study, or if they become pregnant within 30 days (90 days for partners of male subjects) of last Eplastra dose. Subjects who become pregnant or who suspect that they are pregnant must report the information to the Investigator and discontinue study drug immediately. Subjects whose partner has become pregnant or suspects she is pregnant must report the information to the Investigator.

Instructions for reporting pregnancy, partner pregnancy, and pregnancy outcome are outlined in Section 9.8.

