7. Female subject is eligible to enter if it is confirmed that she is:
 - a. Not pregnant or nursing
 - b. Not of childbearing potential (i.e. s/p hysterectomy, oophorectomy or has medically documented ovarian failure, or are postmenopausal women $>$ 50 years of age with cessation of menses for 12 months or greater)
OR
Of childbearing potential with a negative serum pregnancy test within 2 weeks of screening, a negative urine pregnancy test on Day 1, and a commitment to either abstain from intercourse or consistently use an acceptable method of birth control (Appendix 4)

in addition to condom use by her male partner(s) from the date of screening until 30 days after the last dose of study drug

8. All male study participants must agree to consistently and correctly use condoms with their female partner(s) of childbearing potential and such female partner(s) must agree to use an acceptable method of birth control (listed) from the date of screening until 90 days after the last dose of study drug
9. Male subjects must refrain from sperm donation from the date of screening until 90 days after the last dose of study drug
10. Subject must be in generally good health, with the exception of HCV, in the opinion of the Sponsor-Investigator or Sub-Investigator(s)
11. Subject must be able to comply with dosing instructions for study drug administration and able to complete the study visits, including all required post-treatment visits

Exclusion Criteria for clinical subjects:

Subjects who meet any of the following exclusion criteria are not to be enrolled in this study:

1. Presence of decompensated cirrhosis as defined by encephalopathy, ascites, or a history of a variceal bleed
2. Prior treatment with direct acting antiviral hepatitis C medications
3. Positive urine drug toxicity test at screening (except for cannabinoids and prescribed medications)
4. Absence of buprenorphine in urine sample at screening
5. Currently pregnant or breastfeeding female
6. Detectable HIV RNA > 50 copies/ml (co-infected subjects with suppressed viral load ARE eligible for participation)
7. Use of any prohibited concomitant medication within 28 days prior to day 1
8. Chronic use of systemically administered immunosuppressive agents
9. Difficulty with blood collection or poor venous access
10. History of solid organ transplantation
11. Known significant allergy to sofosbuvir or velpatasvir

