6.2 Inclusion Criteria for clinical subjects

1. Willing and able to provide written informed consent
2. Age ≥ 18 years
3. Confirmation of chronic HCV infection as documented by a positive HCV antibody test at least 6 months prior to the Baseline/Day 1 visit OR by patient report of infection for at least 6 months prior to the baseline/day 1 visit AND positive HCV RNA test at screening
4. HCV genotype 1, 2, 3, 4, 5 or 6
5. In stable remission from opioid use on buprenorphine/naloxone for at least 12 weeks

6. Within the following laboratory parameters as assessed at the screening visit:
 - a. HCV RNA quantifiable
 - b. Screening rhythm strip without bradycardia (heart rate > 60 or, if on beta blocker, > 55 BPM)
 - c. ALT \leq 10 x ULN
 - d. AST \leq 10 x ULN
 - e. Direct bilirubin \leq 1.5 x ULN
 - f. Platelets > 60,000
 - g. HbA1c \leq 13%
 - h. Creatinine clearance \geq 30 mL/min, as calculated by the Cockcroft-Gault equation
 - i. Albumin \geq 3g/dL
 - j. INR \leq 1.5 x ULN or on an anticoagulant regimen affecting INR
7. Female subject is eligible to enter if it is confirmed that she is:
 - a. Not pregnant or nursing
 - b. Not of childbearing potential (i.e. s/p hysterectomy, oophorectomy or has medically documented ovarian failure, or are postmenopausal women > 50 years of age with cessation of menses for 12 months or greater)

OR

Of childbearing potential with a negative serum pregnancy test within 2 weeks of screening, a negative urine pregnancy test on Day 1, and a commitment to either abstain from intercourse or consistently use an acceptable method of birth control (Appendix 4) in addition to condom use by her male partner(s) from the date of screening until 30 days after the last dose of study drug
8. All male study participants must agree to consistently and correctly use condoms with their female partner(s) of childbearing potential and such female partner(s) must agree to use an acceptable method of birth control (listed) from the date of screening until 90 days after the last dose of study drug
9. Male subjects must refrain from sperm donation from the date of screening until 90 days after the last dose of study drug
10. Subject must be in generally good health, with the exception of HCV, in the opinion of the Sponsor-Investigator or Sub-Investigator(s)
11. Subject must be able to comply with dosing instructions for study drug administration and able to complete the study visits, including all required post-treatment visits

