8.3.2 Weeks 2, 4, 6, 8, 10 (+/-3 days)

The following procedures/assessments are to be completed:

- Assessment of AEs and concomitant medications
- Obtain blood samples (Reference Study Procedures Table Appendix 2)
- Obtain urine samples (Reference Study Procedures Table Appendix 2)
- Pregnancy testing for women of childbearing potential only (Reference Study Procedures Table Appendix 2)
- Pregnancy Prevention Counseling
- Assess compliance with study drug dosing regimen including pill count
- Download MEMSCap™ Adherence Data
- Dispense study drug supply (weeks 4 and week 8, or as needed for emergency supply)
- Additionally, at week 4 visit only, subject will complete Quality of Life Surveys FACT-F, PROMIS ED -Depression SF8a, SF36)

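### Inclusion 7b and Appendix 5 give opposite childbearing-potential labels to women over 50 and up to 54 with at least 12 months without menses, and inclusion 7 cites the wrong appendix

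*Combined protocol and SAP*

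**What the plan says.** Inclusion 7b appears in the synopsis and in Section 6.2. It places two groups of women in the non-childbearing class. The first group is medical: "s/p hysterectomy, oophorectomy or has medically documented ovarian failure". The second group is set by age and time since last menses, and the text adds it with the words "or are postmenopausal women > 50 years of age with cessation of menses for 12 months or greater".

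Appendix 5 sets a higher age. Its non-childbearing class begins with "Women >54 years of age with cessation for" at least 12 months. It also admits women of any age who have had a hysterectomy, or who "have had both ovaries removed, or have had medically documented ovarian failure will be considered to be of non-childbearing potential". It then covers younger women explicitly: those up to 54 "years of age (including those with amenorrhea of any duration" count as of childbearing potential unless one of the three medical exceptions applies.

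Procedures follow from the label:

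- Appendix 5 itself states: "Women of childbearing potential must have a negative serum pregnancy test at screening and a negative urine pregnancy test" on Day 1. It also requires abstinence or contraception until 30 days after the last dose.
- Section 8.3.2 adds, for each visit from week 2 to week 10, "Pregnancy testing for women of childbearing potential only (Reference Study Procedures Table Appendix 2". Sections 8.3.3 and 8.4.1 add tests at end of treatment and at post-treatment week 4.

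For acceptable birth control methods, inclusion 7 refers the reader to Appendix 4.

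**The concern.** These are two operative definitions in current text, and the protocol gives no order of precedence. The Appendix 5 clause on amenorrhea of any duration rules out reading the two as equivalent.

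The layout favours the looser rule. Section 8.2 sends the eligibility check to Sections 6.2 and 6.3, and no section of the body cites Appendix 5. The one reference that should lead there, in inclusion 7, leads to the grading scale. A site working from Section 6.2 would reasonably label a woman in the disputed age band as not of childbearing potential. It would then omit tests and contraception that Appendix 5 makes mandatory for her.

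What is at stake is subject protection and protocol compliance for a small group. The efficacy analysis is not involved.

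**Working it through.** The plan gives no figure to reproduce. The check compares the two rules and then counts what depends on the label.

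**Step 1. Labels by age.** Take women with at least 12 months without menses and no hysterectomy, oophorectomy or ovarian failure.

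| Age | Inclusion 7b | Appendix 5 | Agree? |
|---|---|---|---|
| 50 or under | childbearing | childbearing | yes |
| over 50, up to 54 | not childbearing | childbearing | **no** |
| over 54 | not childbearing | not childbearing | yes |

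**Step 2. Oophorectomy.** Inclusion 7b does not say one ovary or both; Appendix 5 says both. Read literally, a woman of 54 or younger with one ovary removed is not of childbearing potential under 7b but is under Appendix 5. If 7b means both ovaries, the difference disappears.

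**Step 3. Pointer.** Section 13 and the appendix titles show that Appendix 4 is the grading scale. The contraceptive methods are in Appendix 5.

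**Step 4. Pregnancy tests per woman labelled of childbearing potential.**

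- Required by Appendix 5 itself: 1 serum (screening) + 1 urine (Day 1) = 2.
- Attached to the label by Section 8: 5 (weeks 2, 4, 6, 8, 10) + 1 (end of treatment) + 1 (post-treatment week 4) = 7.
- Total: 2 + 7 = 9.
- In Appendix 2, the end-of-treatment cell can be read as post-treatment week 4 only, though that row may have been broken in extraction. On that reading the total is 9 − 1 = 8.
- Under the 7b label: 0.

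**Step 5. Duration of contraception or abstinence.** Inclusion 7b starts it at screening, Appendix 5 at 3 weeks before Day 1. Starting at the earlier of the two meets both. With 12 × 7 = 84 days of treatment and 30 days afterwards:

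- screening 1 to 21 days before Day 1: 21 + 84 + 30 = 135 days;
- screening 28 days before: 28 + 84 + 30 = 142 days;
- screening extended to 42 days before: 42 + 84 + 30 = 156 days;
- under the 7b label: 0 days.

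**Step 6. Which rule is stricter.** Each of the four non-childbearing classes in Appendix 5 lies inside the matching class in 7b:

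- over 54 with at least 12 months lies inside over 50 with at least 12 months;
- hysterectomy and documented ovarian failure match directly;
- both ovaries removed lies inside oophorectomy.

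A woman whom Appendix 5 labels not of childbearing potential therefore always has that label under 7b too.

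**Step 7. Study total.** The documents do not give the number of affected women. For illustration only, assuming 0, 1 or 2 of about 20, the total is 0, 8 to 9, or 16 to 18 tests.

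**The case against.** The strongest reply is that this is a mismatch between a stricter and a looser rule. One coordinator team at a single centre can handle it by applying the stricter rule, and the title of Appendix 5 announces that it contains the definition. Every woman must be confirmed not pregnant under inclusion 7a whatever her label. Pregnancy is an exclusion in Section 6.3 and a reason to stop drug in Section 5.5. Appendix 5 also reports no embryo-fetal harm in non-clinical studies. These points stand, and they keep the matter minor. They do not tell the site which definition governs.

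A second reply is that 7b covers only postmenopausal women, so the conflict may be narrower than the age band suggests. The protocol defines that word nowhere else. In context it is most naturally read through the 12-month clause that follows it. Even on a narrower reading, postmenopausal women over 50 and up to 54 still get opposite labels.

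Third, beside hysterectomy and ovarian failure, oophorectomy probably means both ovaries. That is fair. This part calls for clarification and is not a firm contradiction.

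Fourth, the stricter label satisfies 7b as a label but can change who is enrolled. A 52-year-old who declines contraception qualifies under 7b and is ineligible under Appendix 5. This is correct and is counted as a cost of the fix.

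**Conclusion.** The concern holds, at minor severity. Two parts are plain errors in current text: the conflicting age limits (over 50 against over 54) and the pointer to Appendix 4. The oophorectomy wording is a third difference only if 7b is read literally.

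For each affected woman the label makes the difference between 8 to 9 tests and none, and between about 135 to 156 days of contraception or abstinence and none. The day counts assume full 12-week treatment and a start at the earlier of the two stated dates. The number of such women is unknown and probably small. The primary endpoint, analysis sets and sample size are unaffected.

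**What to change.** Put one definition, word for word, in the synopsis, Section 6.2 item 7b and Appendix 5. The conservative text would be: *Not of childbearing potential: hysterectomy, removal of both ovaries, medically documented ovarian failure, or age over 54 years with at least 12 months without menses. All other women are of childbearing potential.* The last sentence also places women over 54 with less than 12 months without menses and none of the medical exceptions. Appendix 5 now leaves them in neither class, while 7b leaves them only its childbearing limb.

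The sponsor may instead keep the over-50 limit and change both age limits in Appendix 5 to 50. Either version should state whether oophorectomy means both ovaries. Change the birth control pointer from Appendix 4 to Appendix 5 in the synopsis and Section 6.2. The contraception start dates can stay, since one practice meets both.

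The cost is a wording amendment: the definition in three places and the pointer in two. With the over-54 rule, each reclassified woman takes on the tests and contraception counted above and becomes ineligible if she declines. Reclassified women are those in the disputed age band, and any woman with one ovary removed whom a site would have labelled non-childbearing under 7b. With the over-50 rule, the age change adds no tests, but the protection that Appendix 5 now gives women in the disputed band is given up.

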Appendix 6: HCV Treatment Curriculum
